3.3.2 Definition of truth standard for diagnostic performance

The instrument diagnostic accuracy is measured by sensitivity and specificity on a per-tissue basis. Because a LUM-guided shave does not exist when a negative LUM image is indicated we propose a hierarchical approach to determine the truth standard as depicted in Figure 2. The highest truth standard is whether pathology finds cancer in a tissue shave removed from the area that was imaged in the cavity. When a shave does not exist, then whether tumor is found in a re-excision surgery is considered as the truth standard. When neither a shave nor a second surgery exists for a given orientation that was imaged, the margin assessment of that orientation is used as truth standard. We believe that the hierarchical approach outlined to determine the truth standard is the most meaningful and practical assessment of device accuracy to predict the presence of cancer in the cavity.

LUMICELL CONFIDENTIAL

This document is confidential. Do not disclose or use except as authorized.

True positive = truth standard positive & Lum cavity image positive

False negative = truth standard positive & Lum cavity image negative

True negative = truth standard negative & Lum cavity image negative

False positive = truth standard negative & Lum cavity image positive

Figure 2: Definition of truth standard to evaluate the LUM Imaging System diagnostic performance.

When a therapeutic shave and re-excision are not available for an orientation, the margin from the prior resected tissue of the corresponding orientation will be used as ground inferred truth for evaluation (Figure 3).

The orientation of the tissue removed during a re-excision is typically noted in the pathology report and matches the orientation in which a positive margin was identified from the initial surgery. However, there will be instances in which the orientation of the tissue removed during a re-excision is not specified. In cases of unclear orientation of the tissue removed during re-excisions, it will be assumed that the re-excision was intended to address only the orientations with positive margins and pathology findings from the re-excision (tumor found/not found) will be applied to those orientations.

If a mastectomy is performed as a follow-up surgery and no cancer is found in the mastectomy specimen, all the orientation will be considered as cancer negative for truth standard. If a mastectomy is performed and cancer is found but there is no indication on the orientation in which the cancer was found, the orientation in which a positive margin was identified in the initial lumpectomy will be considered as cancer positive for truth standard unless otherwise noted.

Table 1: Definitions for 2x2 contingency table.

	Truth standard (+)	Truth standard (-)
LUM positive cavity signal (+)	True Positives	False Positives
LUM negative cavity signal (-)	False Negatives	True Negatives

LUMICELL CONFIDENTIAL

This document is confidential. Do not disclose or use except as authorized.

$$sensitivity = \frac{True\ Positives}{True\ Positives + False\ Negatives}$$

$$specificity = \frac{True\ Negatives}{True\ Negatives + False\ Positives}$$

$$Youden\ Index = sensitivity + specificity - 1$$

[figure not shown]

Figure 3: Demonstration of the prior margin for the LUM signal in the cavity,

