### 3.2 Rationale

Achieving negative margins during tumor excision is critical to assure that all or most of the cancer has been removed from the patient. Current standard of care dictates that tissue removed during surgery is analyzed post-operatively for tumor histology and margin assessment by a pathologist as described above. This procedure is time consuming, often requiring 7-10 days of pathology

LUMICELL CONFIDENTIAL

This document is confidential. Do not disclose or use except as authorized.

testing after the operation before margin status is known. In addition, this process is prone to sampling errors, as only a finite number of tissue slices can be examined, meaning that only a small fraction of the lumpectomy margin surface is assessed, < 1% of lumpectomy surface area by some estimates. Thus, a safe method to directly assess the entire tumor bed intraoperatively and identify residual microscopic disease for immediate resection intraoperatively would be highly beneficial for patients.

Lumicell has developed the LUM Imaging System, which consists of a fluorescence-based imaging agent (LUM015), a hand-held, wide-field detector (LUM Imaging Device) that can image the lumpectomy cavity in seconds, and a tumor detection algorithm that highlights regions suspected to contain cancer and displays them on a computer monitor. The LUM Imaging system is intended to be used to scan the lumpectomy cavity walls intraoperatively after the resection of the main lumpectomy specimen.

The Lumicell Imaging System may enable surgeons to achieve negative margins during the initial surgery and eliminate or reduce the need for re-excision surgeries when compared with current standard of care procedures. Lumicell's system images the entire lumpectomy cavity surface *in vivo*, overcoming tissue handling and sampling limitations of standard pathology analysis of resected tissue. The LUM Imaging System provides real-time feedback to the surgeon about the status of the lumpectomy cavity walls, and does not require patient immobilization; hence, the system may not significantly impact surgical workflow.

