## 15.2 Sample size

Analyses during the Phase C study may lead to a change of algorithm (i.e., refinement of the threshold). The tumor detection algorithm will be locked in place before the start of the pivotal study based on the results of this Phase C study. The tumor detection algorithm lock will be contingent on the accrual of enough “pathology positives” to yield a ~7% margin of error in sensitivity. “Pathology positive” is defined as an imaged surface that contains cancer as identified by histopathology. A single patient may give more than one “pathology positive” image. Given that 19 pathology positive samples were acquired during the Phase B study, an additional 32 pathology positives will be needed to achieve the targeted margin of error. Because 40 patients in the Phase B study yielded 19 pathology positives, we expect to image approximately 67 patients during the training portion of the pivotal study (Phase C) before locking the threshold algorithm in place for the pivotal study. However, because the incidence of pathology positives is largely unknown at the sites participating in the future pivotal trial, the study will continue until enough patients have been enrolled to collect the data to lock the tumor detection algorithm. This number of patients will not exceed 250 patients.

Based on our experience from Phase A and Phase B of the feasibility study, we anticipate that with up to 5 patients per surgeon and approximately 1-3 surgeons per site, we may identify and address any site-specific and surgeon-specific issues related to the use of the LUM Imaging System. We anticipate expanding the study to a maximum of 20 sites; thus, we expect to have up to 250 patients in Phase C.

If tumor detection algorithm verification is complete, yet not all surgeons and clinical staff have completed training on the LUM Imaging System, these institutions can continue the training process as a lead-in to any Luminell Imaging Studies they may participate in the future.

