## 15.5 Efficacy and intraoperative imaging data analysis

LUMICELL CONFIDENTIAL

This document is confidential. Do not disclose or use except as authorized.

The tumor detection algorithm optimized during Phase B will be implemented in Phase C to guide the resection of therapeutic SCMs. The imaging data will be compared against histopathology analysis of resected tissue on the side of the tissue where in vivo imaging took place. The data obtained from the different surgeons at each site will be used to further train the tumor detection algorithm. The combined algorithm training data from Phase B and Phase C will be used to estimate the expected results in the pivotal trial to properly power that study.

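### The truth standard for accuracy depends largely on the LUM result, and the SAP reports only pooled sensitivity, specificity and Youden Index, with no breakdown by truth tier and no bias analysis

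*SAP*

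**What the plan says.** SAP 3.3.2 measures accuracy per tissue site against a hierarchical truth standard and gives the reason: "Because a LUM-guided shave does not exist when a negative LUM image is indicated we propose a hierarchical approach". The tiers are:

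1. pathology of a shave taken from the imaged area;
2. if there is no shave, whether a re-excision finds tumour;
3. if there is neither, the margin of the tissue resected earlier at that orientation, which the SAP describes as inferred.

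All tiers enter one 2x2 table (SAP Table 1). SAP 4.3 reports sensitivity, specificity and Youden Index from that table, each with a two-sided 95% interval. No breakdown by tier and no bias or sensitivity analysis is planned. SAP 3.3.1 does plan the lumpectomy margin's own sensitivity and specificity for cancer left in the cavity, as a comparison.

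Protocol 3.2 describes margin pathology as open to sampling error, because "only a small fraction of the lumpectomy margin surface is assessed".

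On precision, Protocol 15.2 asks for enough positives to "yield a ~7% margin of error in sensitivity". Protocol 15.5 says the combined Phase B and Phase C algorithm training data "will be used to estimate the expected results in the pivotal trial to properly power that study".

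**The concern.** The reference standard is not independent of the test under evaluation. This is differential verification, and here it can act in two opposite ways.

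- **Upward.** A LUM-negative orientation with a negative earlier margin and no shave or re-excision can only be scored a true negative, whatever remains in the cavity. Misses of this kind never reach the sensitivity denominator.
- **Downward.** A LUM-negative orientation with a positive margin, a clean cavity and no re-excision is scored a false negative although the device was right.

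The second tier also leans on the margin in places. Under SAP 3.3.2, findings from a re-excision of unclear orientation go to the positive-margin orientations. Cancer of unstated orientation in a mastectomy specimen is treated the same way unless otherwise noted.

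SAP 3.3 marks diagnostic performance as a co-primary endpoint of the pivotal study. A reader will take the Phase C interval as the uncertainty in the device's accuracy, but it covers sampling error only.

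**Working it through.** **1. The plan's own figures reproduce.** The inputs come from Protocol 15.2. In hand: "19 pathology positive samples were acquired during the Phase B study". Still to be collected: "an additional 32 pathology positives will be needed to achieve the targeted margin of error". Yield per patient: "40 patients in the Phase B study yielded 19 pathology positives".

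- Positives: 19 + 32 = 51.
- Patients: 32 / (19/40) = 67.4, against about 67 stated.
- Precision: no formula is named. The exact two-sided 95% lower limit at 51/51 is 0.025^(1/51) = 0.930, or 6.98 points. The Wald half-width at 93% is 1.96 × √(0.93 × 0.07/51) = 7.00 points. Either fits the stated 7%.

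A positive there is "defined as an imaged surface that contains cancer as identified by histopathology". Below, 51 stands in for the number of truth-positive orientations, which is an assumption.

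**2. Both directions in one hypothetical.** All inputs are assumed: 1,000 orientations; 5% with residual cancer; LUM sensitivity and specificity both 80%; margin specificity 95%; every LUM-positive site shaved; no LUM-negative site shaved; shave and re-excision pathology correct; m = margin sensitivity for residual cancer.

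- True positives: 50 × 0.8 = 40. LUM-negative cancers: 10, of which 10m have a positive margin.
- LUM-negative clean sites: 950 × 0.8 = 760, of which 760 × 0.05 = 38 have a positive margin.
- All positive margins re-excised: observed sensitivity = 40/(40 + 10m).
- 80% re-excised: 38 × 0.2 = 7.6 clean sites become false negatives, so observed sensitivity = 40/(40 + 10m + 7.6).

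| m | all re-excised | 80% re-excised |
|---|---|---|
| 0.7 | 85.1% | 73.3% |
| 0.5 | 88.9% | 76.0% |
| 0.3 | 93.0% | 79.1% |

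The true value is 80% throughout. The pooled figure alone cannot show which column applies.

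**3. Two-way tipping point.** Let h be hidden cancers among LUM-negative, margin-negative, otherwise unverified sites. Let r be LUM-negative, margin-positive, never re-excised sites that were in fact clean.

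- Sensitivity(h, r) = TP/(TP + FN + h − r)
- Specificity(h, r) = (TN − h + r)/(TN − h + r + FP)

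With no recorded false negatives (51/51, so r = 0):

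| h | sensitivity |
|---|---|
| 1 | 98.1% |
| 2 | 96.2% |
| 4 | 92.7% |
| 6 | 89.5% |
| 10 | 83.6% |

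Four hidden misses equal the planned margin of error. On 32 Phase C positives alone, three are enough: 32/35 = 91.4%.

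With an assumed 46 true positives and 5 false negatives (90.2%):

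- h = 4, r = 0: 46/55 = 83.6%
- h = 0, r = 2: 46/49 = 93.9%
- h = 4, r = 4: 46/51 = 90.2% again

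Specificity barely moves. With an assumed 450 true negatives and 141 false positives, h = 4 takes it from 450/591 = 76.1% to 446/587 = 76.0%. At 51/51 the Youden Index falls from 76.1% to 68.7%, almost all of it through sensitivity.

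**4. What rate four misses implies.** 40 + 67 = 107 patients × 6 orientations (Protocol 5.3) = 642. If 60% to 85% are LUM-negative with margin-only truth (assumed), that is 385 to 546 sites. Then 4/546 = 0.7% and 4/385 = 1.0%. At an assumed 2% hidden rate, h is 7.7 to 10.9 and 51/51 becomes 87% to 82%.

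**The case against.** **The standard is disclosed and reasoned.** The SAP names the margin tier as inferred, defends the hierarchy as practical, and tests no hypothesis in this study (SAP 1). This stands, and the hierarchy can stay. It does not justify reporting the pooled result alone.

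**The split is not absolute.** SAP 4.8.3 keeps LUM-negative sites that were shaved because of X-ray or pathology, and later standard-of-care shaves that have an image. Conversely, LUM-positive sites where the shave was declined or the shave limit was reached are judged on re-excision or margin. This reduces the problem without removing it.

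**Stronger readings.** A reader might infer four things that the documents do not support.

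- *Sensitivity is inflated.* The working shows that it can go either way.
- *Most LUM-negative orientations rest on the margin alone.* This is plausible. If 1 to 3 of 6 orientations are re-excised in the 17% to 59% of patients with close or positive margins (Protocol 3.1), only about 3% to 30% of orientations reach the second tier. No count by tier is given, however.
- *The pooled figure drives the algorithm lock.* Protocol 15.2 makes the lock contingent on accruing enough positives for the target precision, not on this estimate.
- *The pooled figure powers the pivotal trial.* Protocol 15.5 names the combined algorithm training data and does not cite the SAP hierarchy.

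**A simple correction looks available.** One could divide the margin-verified false negatives by an assumed margin sensitivity. That fails. If every positive margin is re-excised, the margin tier holds no false negatives and the correction is zero. In the 80% re-excised case at m = 0.7, the re-excised false negatives are 7 × 0.8 = 5.6 and the margin-tier ones are 1.4 + 7.6 = 9.0. The corrected value is 40/(40 + 5.6 + 9.0/0.7) = 68.4%, further from the true 80% than the uncorrected 73.3%.

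**Conclusion.** The point holds in a limited form. The truth tier depends largely on the LUM result, the margin tier can err in both directions, and the planned intervals cover neither error. Neither the size nor the net direction can be fixed from the documents. The yardstick is that about four hidden misses at 51/51 equal the whole planned margin of error. Under the assumed 60% to 85% margin-only share, that is 0.7% to 1.0% of such sites. The true sensitivity, margin sensitivity, re-excision share, margin-only share and illustrative 2x2 counts used here are all assumptions. The study is descriptive, so this is a reporting change that should be made; it does not invalidate the design.

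**What to change.** In SAP 4.3:

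1. Beside the pooled 2x2 table, report it by truth tier: shave, re-excision, margin-inferred. Present this as disclosure and not as a replacement estimate, because shave-tier sensitivity is near 100% by design when few LUM-negative sites are shaved.
2. Add a two-way tipping-point analysis. Add h hidden cancers among LUM-negative, margin-negative, otherwise unverified orientations as false negatives. Separately, move LUM-negative, margin-positive, never re-excised orientations from false negative to true negative. Report sensitivity and Youden Index across the grid, and the h that shifts sensitivity by about 7 points. The margin sensitivity already planned in SAP 3.3.1 can inform plausible h if it is computed on shave- or re-excision-verified orientations, since in the margin tier the margin is correct by construction. State that those sites are mainly LUM-positive and may not represent LUM-negative ones.
3. Label the pooled figures as measured against a partly inferred standard, and show the tipping-point range wherever they are used for pivotal planning (Protocol 15.5).

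The cost is SAP wording and two extra tables from data already collected, with no new patients or tissue and no change to surgical procedure. The downside is a possibly wider or less favourable stated sensitivity.

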3.2 Removal of residual cancer (co-primary endpoint in pivotal study)

The first efficacy metric assesses how much additional residual is identified and removed that would have been missed during the initial standard of care procedure. This metric is defined as the ratio of patients who have **residual cancer** found in at least one LUM-guided shave (also known as therapeutic shave or “T-shave”) among all patients. **Residual cancer** is defined as tumor found

LUMICELL CONFIDENTIAL

This document is confidential. Do not disclose or use except as authorized.

by pathology in a therapeutic shave after the SOC surgical procedure is completed; that is, tumor that current SOC surgery failed to remove (Figure 1). Mathematically, it is defined as:

$$\frac{\# \text{ patients with residual cancer found in at least one therapeutic shave}}{\text{Total number of patients}}$$

[figure not shown]

Figure 1: Depiction of removal of residual cancer analysis.

This proposed primary endpoint for determination of whether tumor is found in at least one therapeutic shave, the **ground truth** of histopathology assessment of the therapeutic shave is used

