4.8.2 Multiple images to cover entire shave or multiple shaves for one image

To accurately evaluate the study endpoints, it is critical that images are collected from the entire lumpectomy cavity surface. To achieve this, multiple images may be required to record the LUM assessment for an entire orientation (e.g. 2 images to cover the entire superior orientation) but a single shave may exist. When multiple images exist for a given orientation or shave, the combination of the images will be considered as one single output as described below:

- All images for a given orientation or shaved region are LUM negative, then the LUM result for the entire orientation or shaved region is considered as LUM negative.

LUMICELL CONFIDENTIAL

This document is confidential. Do not disclose or use except as authorized.

- If one or more of the images for a given orientation or shaved region is LUM positive, then the LUM result for the entire orientation or shaved region is considered as LUM positive.

When there are more than one shave for a single image, the pathology finding for the combination of the shaves will be considered as one as follows:

- If no tumor is found on the shaves, then the combination of the shaves is considered as truth standard negative.
- If any of the shaves has tumor, then the combination of the shaves is considered as truth standard positive.

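### SAP 3.3.2 gives conflicting truth standards for a tumour-bearing shave when the patient later has a clean mastectomy

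*SAP*

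**What the plan says.** SAP 3.3.1 says that sensitivity, specificity and the Youden Index use a hierarchical truth standard, and 3.3.2 sets it out in three tiers:

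- Tier 1, shave pathology: "The highest truth standard is whether pathology finds cancer in a tissue shave removed from the area that was imaged in the cavity".
- Tier 2, second surgery: "When a shave does not exist, then whether tumor is found in a re-excision surgery is considered as the truth standard".
- Tier 3, margin: "When neither a shave nor a second surgery exists for a given orientation that was imaged, the margin assessment of that orientation is used" as the truth.

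SAP 4.8.2 follows the same principle where several shaves correspond to one image: "If any of the shaves has tumor, then the combination of the shaves is considered as truth standard positive".

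Later in 3.3.2 comes the rule for a follow-up mastectomy. Where "no cancer is found in the mastectomy specimen, all the orientation will be considered as cancer negative for truth standard". It makes no exception for orientations that already have a shave.

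A neighbouring rule in 3.3.2 covers re-excisions whose orientation is not recorded. They are assumed to address only the positive-margin orientations, and "pathology findings from the re-excision (tumor found/not found) will be applied to those orientations". This rule does not mention shaves either.

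SAP 3.2 counts a patient as having residual cancer when pathology finds tumour in at least one therapeutic shave, described as "tumor that current SOC surgery failed to remove".

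**The concern.** A mastectomy specimen shows the breast after the shaves have been taken out. A clean specimen is what complete removal would produce, so it cannot show that a shave in which pathology found tumour came from a cancer-free site. If the mastectomy rule is applied to every orientation, it replaces the best evidence about the imaged surface with evidence about what remained after that surface was removed.

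Two metrics would then disagree about the same tissue. A therapeutic shave with tumour would be residual cancer in 3.2 and cancer-negative in 3.3. The SAP labels both as co-primary endpoints in the pivotal study.

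The situation is foreseeable. Protocol 8.5 names mastectomy as a possible second surgery for positive margins. SAP 4.8.3 (d) and (g) keep LUM-negative images with a shave taken for other reasons in the sensitivity and specificity analysis, so misses proven by a shave can exist.

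Protocol 15.5 uses the combined Phase B and Phase C data to estimate expected results for the pivotal trial and to power it. The study is open label (Protocol 1), so a choice between readings left to the programming stage could be made with results in view.

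**Working it through.** The documents give no figure for this rule, so there is none to reproduce. The check is a comparison of classifications, followed by an illustration of size.

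**Step 1: classify every case.** Take one imaged orientation in a patient whose follow-up mastectomy is clean. It is LUM-positive or LUM-negative; its shave contains tumour, is clean, or does not exist; its margin is positive or negative. That gives 2 × 3 × 2 = 12 cells. Reading A applies the hierarchy, with mastectomy as second surgery. Reading B applies the mastectomy sentence literally. The labels follow the SAP definitions, for example "False positive = truth standard negative & Lum cavity image positive". Margin status changes nothing under either reading, so each row below stands for two cells.

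| LUM | Shave | Reading A | Reading B |
|---|---|---|---|
| + | tumour | true positive | false positive |
| − | tumour | false negative | true negative |
| + | clean | false positive | false positive |
| − | clean | true negative | true negative |
| + | none | false positive | false positive |
| − | none | true negative | true negative |

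The readings differ in 4 of 12 cells, all with a tumour-bearing shave. In the last row, a LUM-negative orientation with a positive margin and no shave is truth-negative under the hierarchy as well, because second surgery outranks the margin. The conflict does not touch it.

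**Step 2: direction.** Let P be the number of truth-positives.

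- Recoding one true positive changes sensitivity by (TP − 1)/(P − 1) − TP/P = −FN/[P(P − 1)]. It also adds a false positive, so specificity falls.
- Recoding one false negative changes sensitivity by TP/(P − 1) − TP/P = +TP/[P(P − 1)]. It also adds a true negative, so specificity rises.

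The net direction depends on which kind occurs.

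**Step 3: illustration.** Protocol 15.2 plans 19 + 32 = 51 pathology positives over Phases B and C. I use 51 only to set the scale, because the protocol counts imaged surfaces and the SAP counts orientations. The rest of the table is assumed: TP 43, FN 8, TN 298, FP 52.

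| Cells recoded | Sensitivity | Specificity | Youden |
|---|---|---|---|
| None | 43/51 = 84.3% | 298/350 = 85.1% | 0.695 |
| 1 TP to FP | 42/50 = 84.0% | 298/351 = 84.9% | 0.689 |
| 3 TP to FP | 40/48 = 83.3% | 298/353 = 84.4% | 0.678 |
| 1 FN to TN | 43/50 = 86.0% | 299/351 = 85.2% | 0.712 |
| 3 FN to TN | 43/48 = 89.6% | 301/353 = 85.3% | 0.749 |

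The formula agrees: one recoded miss adds 43/(51 × 50) = 1.7 points of sensitivity, and one recoded true positive removes 8/(51 × 50) = 0.3 points.

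On the scale of the 32 positives planned for Phase C alone, with 29 assumed detected, one recoded miss moves sensitivity from 29/32 = 90.6% to 29/31 = 93.5%.

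**The case against.** The strongest reply is that the precedence is already stated. The hierarchy opens the same subsection and puts shave pathology first, 3.3.1 says the metrics follow it, and 4.8.2 agrees. The mastectomy text comes straight after the paragraph on unoriented re-excisions, and its companion sentence deals with cancer found in a mastectomy without a stated orientation. Both can be read as explaining how to assign an unoriented second specimen to orientations within the second-surgery tier. On that reading the rule covers only orientations settled by second surgery, and a tumour-bearing shave stays positive. Figure 2, which is not visible in the text reviewed, may show this order.

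This stands as far as it goes. A reader might infer that the SAP has deliberately chosen to let a clean mastectomy override a tumour-bearing shave. The documents do not support that: no sentence says so, and the hierarchy points the other way.

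It does not remove the conflict. The mastectomy sentence is the more specific rule, comes later and covers all orientations. Its companion sentence is limited to positive-margin orientations and allows exceptions. Elsewhere in 3.3.2 the SAP writes the no-shave condition out when it wants it. A programmer following the sentence as written would misclassify.

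Two further replies also stand. Recoded misses are a narrow group: a LUM-negative image, a shave taken anyway, tumour in it, then a clean mastectomy. And most of the illustrated shifts are small beside the margin of error of about 7% in sensitivity targeted in Protocol 15.2. SAP 1 confirms that no hypothesis-tested endpoint was pre-defined, so no test decision turns on this.

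**Conclusion.** SAP 3.3.2 contains an unresolved contradiction, confined to orientations with a tumour-bearing shave in patients whose follow-up mastectomy is clean. The literal reading gives the wrong class there and contradicts the residual-cancer metric in 3.2.

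The size is unknown. The documents give no mastectomy rate and no count of such shaves, and the effect is zero if no such patient occurs. In the illustration, one to three recoded orientations move sensitivity down by 0.3 to 1.0 points or up by 1.7 to 5.3 points, depending on the kind. Every count except the planned positives is assumed.

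Two wider inferences are tempting and not supported. One is that all the accuracy figures are wrong in these patients: 8 of the 12 cells are the same under both readings. The other is that these patients are especially likely to have tumour-bearing shaves: no figure supports it, and the group is selected for having no cancer in the mastectomy specimen.

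The rule for re-excisions of unclear orientation has the same gap in its wording, as a secondary matter. It matters only where a positive-margin orientation also has a tumour-bearing shave and the unoriented re-excision is clean. The SAP says that orientation is usually recorded.

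**What to change.** In SAP 3.3.2, limit the clean-mastectomy rule to imaged orientations with no shave from the imaged area. State beside it that wherever such a shave exists, its pathology remains the truth standard whatever a later mastectomy or re-excision shows. As a secondary change, put the same limit on the rule for re-excisions of unclear orientation. If Figure 2 shows the order of the branches, check that it agrees.

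This follows the SAP's own hierarchy. It costs one clause in each rule and one programming condition, and needs no new data. A listing of any orientations with a tumour-bearing shave followed by a clean mastectomy or a clean unoriented re-excision would show whether the point affects any result.
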